4.2 Exclusion Criteria

The presence of any of the following will exclude a subject from study enrollment:

4.2.1 Prior treatment with any BTK inhibitor

- 4.2.2 Subjects receiving any other investigational agents or participating in another therapeutic clinical trial.
- 4.2.3 Subjects with active (treated or untreated) brain metastases/ central nervous system (CNS) disease (including but not limited to CNS PTLD) will be excluded from this clinical trial
- 4.2.4 Prior malignancy (or any other malignancy that requires active treatment), except for adequately treated basal cell or squamous cell skin cancer, in situ cervical cancer, early stage prostate cancer or other cancer from which the subject has been disease free for \geq 3 years
- 4.2.5 Clinically significant cardiovascular disease such as uncontrolled or symptomatic arrhythmias, congestive heart failure, or myocardial infarction within 6 months of screening, or any Class 3 or 4 cardiac disease as defined by the New York Heart Association Functional Classification. Subjects with controlled, asymptomatic atrial fibrillation during screening can enroll in the study.
- 4.2.6 Has difficulty with or is unable to swallow oral medication, or has significant gastrointestinal disease that would limit absorption of oral medication.
- 4.2.7 Known history of infection with HIV. HIV-positive subjects on combination antiretroviral therapy are ineligible because of the potential for pharmacokinetic interactions with acalabrutinib.
- 4.2.8 Patients with uncontrolled concurrent illness like active infection (eg, bacterial, viral, or fungal) requiring IV antibiotics or psychiatric illness/social situations that would limit compliance with study requirements
- 4.2.9 Known history of drug-specific hypersensitivity or anaphylaxis to acalabrutinib or rituximab (including active product or excipient components).
- 4.2.10 Active bleeding, history of bleeding diathesis (eg, hemophilia or von Willebrand disease).
- 4.2.11 Uncontrolled AIHA (autoimmune hemolytic anemia) or ITP (idiopathic thrombocytopenic purpura).
- 4.2.12 Requires treatment with a strong cytochrome P450 3A4 (CYP3A4) inhibitor/inducer
- 4.2.13 Requires or receiving anticoagulation with warfarin or equivalent vitamin K antagonists (eg, phenprocoumon)
- 4.2.14 Requires treatment with proton pump inhibitors (eg, omeprazole, esomeprazole, lansoprazole, dexlansoprazole, rabeprazole, or pantoprazole). Subjects receiving proton pump inhibitors who switch to H2-receptor antagonists or antacids are eligible for enrollment to this study.
- 4.2.15 History of significant cerebrovascular disease or event, including stroke or intracranial hemorrhage, within 6 months before the first dose of study drug.
- 4.2.16 Major surgical procedure within 28 days of first dose of study drug. Note: If a subject had major surgery, they must have recovered adequately from any toxicity and/or complications from the intervention before the first dose of study drug.
- 4.2.17 Hepatitis B or C serologic status: subjects who are hepatitis B core antibody (anti-HBc) positive and who are surface antigen negative will need to have a negative polymerase chain reaction (PCR). Those who are hepatitis B surface antigen (HbsAg) positive or hepatitis B PCR positive will be excluded. Subjects who are hepatitis C antibody positive will need to have a negative PCR result. Those who are hepatitis C PCR positive will be excluded.
- 4.2.18 History of progressive multifocal leukoencephalopathy (PML)
- 4.2.19 Breastfeeding or pregnant. Pregnant or breastfeeding women are excluded from this study because it is unknown how acalabrutinib and rituximab can affect the fetus or infant. Rituximab can cross the placenta and is found in breast milk. Acalabrutinib

has been found in the breast milk of animals and there is not significant data regarding its effect during pregnancy.

4.2.20 Vaccination with live virus vaccines is not allowed within 4 weeks of study treatment of or during treatment.

4.2.21 Active GVHD requiring treatment

4.2.22 Patients with biopsy proven transplant organ rejection that is clinically significant as determined by transplant team

4.3 Inclusion of Women and Minorities

Men, women and members of all races and ethnic groups are eligible for this trial.

5.0 Registration

All subjects who have been consented are to be registered in the OnCore™ Database. For those subjects who are consented, but not enrolled, the reason for exclusion must be recorded.

All subjects will be registered through Cleveland Clinic and will be provided a study number by emailing the Study Coordinator with the contact information provided on page 2 of this document.

6.0 Treatment Plan

6.1

Table 2: Treatment Regimen Overview

Cycle	Agent	Suggested Premedication³	Dose	Route	Schedule	Cycle Length
Cycle 1	Rituximab	Acetaminophen (650 mg) PO and diphenhydramine (50 mg) PO or IV, 30 -60 minutes prior to each infusion ¹ .	375mg/m ² IV or 1400mg SC	IV or subcutaneous (SC)	Days 1,8,15,22	
Cycle 2 for subjects in CR	Rituximab	Acetaminophen (650 mg) PO and diphenhydramine (50 mg) PO or IV, 30 -60 minutes prior to each infusion ¹ .	375mg/m ² IV or 1400mg SC	IV or subcutaneous (SC)	Days 1,8,15,22	28 days
Cycles 2-4 for subjects in PR	Rituximab	Acetaminophen (650 mg) PO and diphenhydramine (50 mg) PO or IV, 30 -60 minutes prior to each infusion ¹ .	375mg/m ² IV or 1400mg SC	IV or subcutaneous (SC)	Day 1	
Cycles 1-4	Acalabrutinib	none	100mg BID	PO	Days 1-28	

1. Hydroxyzine may be substituted in patients intolerant of diphenhydramine
2. First dose of rituximab will be given IV and subsequent doses can be either IV or SC based on institutional guidelines.
3. Premedication can be per institutional standards or as suggested above

If a patient is on immunosuppressants, the treating physician will discuss with the transplant team about reducing immunosuppression according to local institutional standard of care. If the transplant team decides to reduce the immunosuppression, the study treatment can be started simultaneously and it is not required to fail the trial of immunosuppression to start the study treatment. If the transplant team deems that it is not safe to reduce the immunosuppression, eligible patients can start study treatment.

6.1.1 Criteria for starting a new cycle

The following treatment parameters should be met on D1 prior to initiating a new cycle (starting with cycle 2):

- ANC $\geq 500/\text{mcL}$
- Platelets $\geq 50,000/\text{mcL}$ (if there is documented bone marrow involvement or hypersplenism, then platelets $\geq 25,000/\text{mcL}$)
- Any non-hematologic grade 3 or 4 AE that is considered at least possibly related to study treatment that has resolved to Grade ≤ 1 .

Growth factors can be used as per institutional standard to treat/prevent neutropenia. The use of growth factors should be documented in the CRF.

6.1.2 Acalabrutinib Administration

Patients will receive acalabrutinib 100mg BID orally on days 1-28. See Table 2 above for further details. Also refer to the drug diary (appendix IV) for further directions. On days with rituximab administration, acalabrutinib may be taken first in order to allow 12 hours between dosing.

The capsules should be swallowed intact with water. Subjects should not attempt to open capsules or dissolve them in water. Acalabrutinib can be taken with or without food.

If a dose is missed, it can be taken up to 3 hours after the scheduled time with a return to the normal schedule with the next dose. If it has been > 3 hours, the dose should not be taken and the subject should take the next dose at the scheduled time. The missed dose will not be made up and must be returned to the site at the next scheduled visit.

Drug interactions for Acalabrutinib are described in Section 6.3.

Appropriate dose modifications for Acalabrutinib are described in Section 7.0.

Reported adverse events and potential risks of Acalabrutinib are described in Section 8.0.

6.1.3 Rituximab Administration

Patients will receive Rituximab on days 1, 8, 15, and 22 of 28 day cycles during cycle 1 and day 1 (for PR responders) or days 1, 8, 15, and 22 (for CR responders) of subsequent cycles (see Table 2 above). First dose will be administered IV per institutional standard and subsequent doses can be given either IV or SQ per institutional guidelines. CAUTION: DO NOT ADMINISTER AS AN INTRAVENOUS PUSH OR BOLUS. See Table 2 above for further details.

Rituximab biosimilar use is permitted for this study per treating investigator discretion or per insurance mandate.

Appropriate dose modifications for Rituximab are described in Section 7.0. Reported adverse events and potential risks of Rituximab are described in Section 8.0.

6.2 Duration of Therapy

See Section 3.4

6.3 General Concomitant Medications and Supportive Care Guidelines

Subjects should receive full supportive care, including transfusions of blood and blood products, antibiotics, antiemetics, etc when appropriate.

Patients with hepatitis B core antibody positive and HBV viral DNA PCR negative should receive prophylaxis with either lamivudine or entecavir (per institutional standard) while receiving rituximab and for 6 months after last dose of rituximab

Any chemotherapy, anticancer immunotherapy (other than Rituximab), corticosteroids (at dosages equivalent to prednisone > 20 mg/day for longer than 2 weeks), experimental therapy (other than acalabrutinib), or radiotherapy for treating PTLD are prohibited.

Warfarin or equivalent vitamin K antagonists (eg, phenprocoumon) are prohibited.

The concomitant use of strong inhibitors/inducers of CYP3A4 (see Appendix 2) should be avoided when possible. If a subject requires a strong CYP3A inhibitor while on study, monitor the subject closely for potential toxicities.

Subjects should avoid the use of calcium carbonate-containing drugs or supplements for a period of at least 2 hours before and at least 2 hours after taking acalabrutinib. H2-receptor antagonists should be avoided or taken hours after taking acalabrutinib. H2-receptor antagonists should be taken approximately 2 hours after an acalabrutinib dose. Use of omeprazole, esomeprazole, lansoprazole or any other proton pump inhibitors while taking acalabrutinib is not recommended due to a potential decrease in study drug exposure. However, the decision to treat with proton-pump inhibitors during the study is at the investigator's discretion, with risks and benefits reviewed.

6.3.1 Drug-Drug Interactions with Acalabrutinib

At the systemic exposure levels expected in this study, acalabrutinib inhibition of CYP metabolism is not anticipated.

However, acalabrutinib is metabolized by CYP3A. Concomitant administration of acalabrutinib with a strong CYP3A and P-glycoprotein (P-gp) inhibitor, itraconazole increased exposure by approximately 5-fold. Conversely, concomitant administration of acalabrutinib with a strong CYP3A inducer, rifampin decrease acalabrutinib exposure and could reduce efficacy. Consequently, the concomitant use of strong inhibitors/inducers of CYP3A (see Appendix 2) should be avoided when possible.

If medically justified, subjects may be enrolled if such inhibitors or inducers can be discontinued or alternative drugs that do not affect these enzymes can be substituted within 7 days before first dose of study drug. If a subject requires a strong CYP3A4 while on study, the subject should be monitored closely for any potential toxicities.

The effect of agents that reduce gastric acidity (eg, proton pump inhibitors or antacids) on acalabrutinib absorption was evaluated in a healthy volunteer study (ACE-HV-004). Results from this study indicate that subjects should avoid the use of calcium carbonate-containing drugs or supplements for a period of at least 2 hours before and at least 2 hours after taking acalabrutinib. Use of omeprazole, esomeprazole, lansoprazole or any other proton pump inhibitors while taking acalabrutinib is not recommended due to a potential decrease in study

drug exposure. However, the decision to treat with proton-pump inhibitors during the study is at the investigator's discretion, with an understanding of the potential benefit to the subject's gastrointestinal condition and a potential risk of decreased exposure to acalabrutinib.

Although the effect of H2-receptor antagonists (such as famotidine or ranitidine) on acalabrutinib absorption has not been evaluated, if treatment with an H2-receptor antagonist is required, the H2-receptor antagonist should be taken approximately 2 hours after an acalabrutinib dose.

6.3.2 Drug-Drug Interactions with Rituximab

No known drug-drug interactions. However, limited data are available on the safety of the use of biologic agents or disease modifying antirheumatic drugs (DMARDs) other than methotrexate in RA patients exhibiting peripheral B-cell depletion following treatment with rituximab. Observe patients closely for signs of infection if biologic agents and/or DMARDs are used concomitantly

6.4 Criteria for Removal from Study

Treatment may continue for 2-4 cycles or until one of the following criteria applies:

- Disease progression
- Development of second primary malignancy
- Intercurrent illness that prevents further administration of treatment
- The investigator considers it, for safety reasons, to be in the best interest of the subject
- Unacceptable adverse event(s) (Any toxicity or other issue that causes a delay of study drug administration by more than 4 weeks)
- Subject decision to withdraw from treatment (partial consent) or from the study (full consent),
- Pregnancy during the course of the study for a child-bearing participant
- Death
- Sponsor reserves the right to temporarily suspend or prematurely discontinue this study.

The date and reason for discontinuation must be documented. Every effort should be made to complete the appropriate assessments.

6.5 Duration of Follow Up

End of Treatment Response Assessment: End of treatment scans and visit will be completed within 8 weeks (± 7 days) of treatment termination. Subjects with stable or progressive disease after Cycle 1 Day 36 scans will go directly onto LTFU.

If there is an adverse event related to study drug, the clinical course of each event will be followed until resolution, stabilization, or until it has been determined that the study treatment or participation is not the cause with a cut off of 24 months after completion of therapy.

Serious adverse events that are still ongoing at the end of the study period will necessitate follow-up to determine the final outcome. Any serious adverse event that occurs after the study period and is considered to be possibly related to the study treatment or study participation will be recorded and reported immediately.

Long-Term Follow Up

Each subject should be followed for a total of 3 years after study treatment has ended. Follow up visits will occur at 6, 12, 18, 24 and 36 months after completion of treatment. During this period, subjects will be followed via physical exam and laboratory analysis. CT scans will be repeated at 6, 12, and 24 months. If the patient is unable to follow up in person, virtual visits may be used to capture applicable procedures during long-term follow up only. Subjects who

experience disease progression are not required to come in for clinic follow up. Study team will make every effort to contact them via phone to obtain information specified in the protocol (see section 11.1.2).

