3.4 Expected Duration of Treatment and Subject Participation

Duration of treatment will depend on patients' response to therapy. Initial treatment (cycle 1) for all patients, will be 28 days in length. Between days 39-42 after the end of cycle 1 treatment, patients will undergo CT scan for response assessment. Patients with a complete response will receive one additional 28 day cycle of therapy. Patients with a partial response will receive 3 additional 28 day cycles of therapy. Patients with stable disease or progressive disease will come off study treatment and go directly on to long-term follow-up. Patients will receive a minimum of 1 cycle of therapy and a max of 4 cycles depending on their response. Cycle 2 should start within 2 weeks after the end of cycle 1 treatment.

Table 1: Total Duration of Treatment Based on Disease Response

Response to Cycle 1	Duration of Treatment
Complete Response	56 days
Partial Response	112 days
Stable or Progressive Disease	28 days

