7.0 Dose Delays/Dose Modifications

7.1 Acalabrutinib

Subjects should be followed closely for AEs or laboratory abnormalities that might indicate acalabrutinib-related toxicity. If a subject experiences an acalabrutinib-related toxicity or other intolerable AE during the course of therapy, then acalabrutinib should be withheld, as necessary, until the AE resolves or stabilizes to an acceptable degree.

Dose modifications for the following acalabrutinib-emergent toxicities are provided in Table 3:

- Grade 4 neutropenia (< 500/ μ L) for > 7 days
- Grade 3 thrombocytopenia in presence of significant bleeding.
- Grade 4 thrombocytopenia.
- Grade 3 or 4 nausea, vomiting, or diarrhea, if persistent despite optimal antiemetic and/or anti-diarrheal therapy.
- Any other Grade 4 toxicity or unmanageable Grade 3 toxicity.

Table 3: Drug Modification Actions for Acalabrutinib

Occurrence	Action
1 st	Hold acalabrutinib until recovery to Grade 1 or baseline; may restart at original dose level
2 nd	Hold acalabrutinib until recovery to Grade 1 or baseline; restart at lower dose 100 mg daily
3 rd	For non-hematologic AE's, discontinue acalabrutinib. For thrombocytopenia with significant bleeding, discontinue acalabrutinib. For other hematologic AEs, hold acalabrutinib until recovery to Grade 1 or baseline; restart at lower dose 100 mg daily .
4 th	For hematologic AEs, discontinue acalabrutinib

Acalabrutinib may be held for a maximum of 28 consecutive days from expected dose due to toxicity. During this period, appropriate laboratory monitoring should be performed per institutional guidelines. As appropriate, certain laboratory abnormalities may warrant more frequent monitoring (eg, once per week) until abnormalities have recovered to Grade 1. Acalabrutinib should be discontinued in the event of a grade 3 or 4 toxicity considered at least possibly related lasting >28 days.

If acalabrutinib is reduced for apparent acalabrutinib-related toxicity, the dose need not be re-escalated, even if there is minimal or no toxicity with the reduced dose. However, if the subject tolerates a reduced dose of acalabrutinib for \geq 4 weeks then the dose may be increased to the next higher dose level, at the discretion of the investigator and after discussion with the sponsor-investigator. Such re-escalation may be particularly warranted if further evaluation reveals that the AE that led to the dose reduction was not treatment-related. The maximum dose of acalabrutinib is 100 mg BID.

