8.1.1.3 Cytopenias

Treatment-emergent Grade 3 or 4 cytopenias including neutropenia, anemia, and thrombocytopenia have occurred in clinical studies with acalabrutinib. Subjects should be closely monitored as appropriate.

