8.5 Reporting Procedures for Serious Adverse Events and AESIs

For the purposes of safety reporting, all adverse events will be reported that occur on or after Cycle 1 Day 1 through the End of Treatment Response Assessment. Adverse events, both serious and non-serious, and deaths that occur during this period will be recorded in the source documents. All SAEs/AESIs should be monitored until they are resolved or are clearly determined to be due to a subject's stable or chronic condition or intercurrent illness(es). Related AEs will be followed until resolution to baseline or grade 1 or stabilization.

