11.1.2 Treatment Period

Cycle 1 is 28 days followed by interim response assessment at day 42 (- 3 day window)

Cycle 2 (in patients with CR is 28 days)

Cycles 2-4 (in patients with PR is 28 days)

Cycle 1, Day 1

- Physical Examination
- Weight
- Vital signs including: blood pressure, pulse, respiratory rate and temperature.
- Concurrent Medications Assessment including prescription medications, over-the-counter (OTC) medications and natural/herbal supplements.
- ECOG performance status
- Laboratory Studies:
 - Complete Blood Count (CBC) with differential and platelets.

- Serum Chemistries: Serum chemistry panel: sodium, potassium, chloride, bicarbonate, BUN, creatinine, calcium, glucose, total protein, albumin, alkaline phosphatase, total bilirubin, SGOT [AST], SGPT [ALT]
 - LDH, uric acid, phosphorous
- Rituximab IV administration
- Acalabrutinib started (days 1 – 28)
- Adverse event evaluation and documentation

Cycle 1, Day 8 ± 2 days

- Vital signs including: blood pressure, pulse, respiratory rate and temperature.
- Laboratory Studies:
 - Complete Blood Count (CBC) with differential
- Rituximab administration
- Adverse event evaluation and documentation

Cycle 1, Day 15 ± 2 days

- Vital signs including: blood pressure, pulse, respiratory rate and temperature.
- Laboratory Studies:
 - Complete Blood Count (CBC) with differential
 - Serum Chemistries: Serum chemistry panel: sodium, potassium, chloride, bicarbonate, BUN, creatinine, calcium, glucose, total protein, albumin, alkaline phosphatase, total bilirubin, SGOT [AST], SGPT [ALT]
- Rituximab administration
- Adverse event evaluation and documentation

Cycle 1, Day 22 ± 2 days

- Vital signs including: blood pressure, pulse, respiratory rate and temperature.
- Laboratory Studies:
 - Complete Blood Count (CBC) with differential
- Rituximab administration
- Adverse event evaluation and documentation

Cycle 1, Day 42 (-3 day window)

- CT scan of neck, chest, abdomen, and pelvis with IV and PO contrast. CT neck can be omitted if there was no involvement at baseline
- Interim disease response assessment
- Peripheral blood EBV PCR if positive at baseline
- Adverse event evaluation and documentation
- Peripheral blood sample for correlative studies

Cycle 2, Day 1 (for CR responders ONLY)

Cycle 2 should start within 2 weeks after the end of cycle 1 treatment.

- Physical Examination
- Weight
- Vital signs including: blood pressure, pulse, respiratory rate and temperature

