- Concurrent Medications Assessment including prescription medications, over-the-counter (OTC) medications and natural/herbal supplements.
- ECOG Performance Status
- Adverse event evaluation and documentation

- Laboratory Studies:
 - Complete Blood Count (CBC) with differential and platelets
 - Serum Chemistries: Serum chemistry panel: sodium, potassium, chloride, bicarbonate, BUN, creatinine, calcium, glucose, total protein, albumin, alkaline phosphatase, total bilirubin, SGOT [AST], SGPT [ALT]
 - Lactate dehydrogenase (LDH)
- Rituximab administration on days 1, 8, 15, and 22
- Acalabrutinib on days 1-28

Cycles 2-4, Day 1 (for PR responders ONLY)

Cycle 2 should start within 2 weeks after the end of cycle 1 treatment. There is a \pm 3 day window for the start of cycles 3 and 4.

- Physical Examination
- Weight
- Vital signs including: blood pressure, pulse, respiratory rate and temperature
- Concurrent Medications Assessment including prescription medications, over-the-counter (OTC) medications and natural/herbal supplements.
- ECOG Performance Status
- Adverse event evaluation and documentation
- Laboratory Studies:
 - Complete Blood Count (CBC) with differential and platelets
 - Serum Chemistries: Serum chemistry panel: sodium, potassium, chloride, bicarbonate, BUN, creatinine, calcium, glucose, total protein, albumin, alkaline phosphatase, total bilirubin, SGOT [AST], SGPT [ALT]
 - Lactate dehydrogenase (LDH) only on cycle 2 day 1 (not required on cycles 3-4)
- Rituximab administration on day 1
- Acalabrutinib started (continue days 1-28)

End of Treatment Response Assessment – 8 weeks \pm 7 days after treatment completion (this

visit does not apply to subjects with stable/progressive disease after cycle 1)

- Physical Examination
- Weight
- Vital signs including: blood pressure, pulse, respiratory rate and temperature.
- Concurrent Medications Assessment including prescription medications, over-the-counter (OTC) medications and natural/herbal supplements.
- ECOG Performance Status
- Adverse Event Evaluation
- Laboratory Studies:
 - Complete Blood Count (CBC) with differential and platelets.
 - Serum Chemistries: albumin, alkaline phosphatase, total bilirubin, bicarbonate, BUN, calcium, chloride, creatinine, glucose, potassium, total protein, SGOT [AST], SGPT [ALT], sodium
 - Lactate dehydrogenase (LDH)
 - Peripheral blood EBV PCR if positive at baseline

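### Patients with stable or progressive disease after cycle 1 have no scheduled blood count after day 22 and no chemistry after day 15 until month 6 at the earliest

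*Combined protocol and SAP*

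**What the plan says.** Every patient takes acalabrutinib on days 1-28 of cycle 1 (6.1.2), with rituximab on days 1, 8, 15 and 22. Section 11.1.2 schedules CBC at each of those four visits and chemistry on days 1 and 15. The Day 42 (-3) visit lists CT, response assessment, EBV PCR if positive at baseline, adverse event evaluation and a correlative blood sample. The calendar in 11.2 agrees: the CBC and chemistry rows are empty in the Day 42 column.

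For patients with stable disease (SD) or progressive disease (PD), section 3.4 says: "Patients with stable disease or progressive disease will come off study treatment and go directly on to long-term follow-up". Section 6.5 repeats this: "Subjects with stable or progressive disease after Cycle 1 Day 36 scans will go directly onto LTFU". Of the End of Treatment assessment, which includes both tests, 11.1.2 says that the "visit does not apply to subjects with stable/progressive disease after cycle 1".

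Long-term follow-up lists CBC and chemistry from month 6. Section 11.1.2 excuses both SD and PD patients from clinic attendance and allows a telephone contact on survival, disease status and lymphoma treatment. Section 6.5 and calendar footnote h excuse only those with progression.

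Elsewhere, 7.1 says: "Subjects should be followed closely for AEs or laboratory abnormalities that might indicate acalabrutinib-related toxicity". Section 8.1.1.3, on cytopenias, says: "Subjects should be closely monitored as appropriate". Section 8.5 adds: "Related AEs will be followed until resolution to baseline or grade 1 or stabilization".

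**The concern.** The last scheduled laboratory tests come before the end of dosing, and patients who stop after cycle 1 have none scheduled soon afterwards. Responders are tested again at cycle 2 day 1 and about 8 weeks after treatment. SD and PD patients have neither visit.

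Day 42 is also the last defined safety visit for SD and PD patients. Adverse events are collected through the End of Treatment assessment (8.5), which they do not have. At Day 42 they have an adverse event evaluation and a blood draw, but no safety laboratory test.

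At stake is the detection of a cytopenia, or of renal or hepatic toxicity, that causes no symptoms and begins or persists after the last test. The chemistry gap is the wider one. Section 8.2.1.4 asks for close watch for renal failure and action on a rising creatinine, yet the last cycle 1 chemistry precedes the day 22 rituximab dose.

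**Working it through.** The plan states no figure to reproduce here. The check compares the visit lists with the calendar and counts days from cycle 1 day 1, as 11.1.2 does.

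**1. Scheduled tests from the start of treatment (11.1.2 and 11.2)**

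| Test | Cycle 1 | Day 42 (-3) | Cycle 2 day 1 | End of Treatment | Month 6 |
|---|---|---|---|---|---|
| CBC | days 1, 8, 15, 22 | none | CR/PR only | CR/PR only | listed; SD/PD need not attend (11.1.2) |
| Chemistry | days 1, 15 | none | CR/PR only | CR/PR only | listed; SD/PD need not attend (11.1.2) |

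**2. Dosing days after the last test.** Dosing ends on day 28; the day 15 and day 22 visits have a window of ±2 days.
- CBC: 28 - 22 = 6 days (28 - 24 = 4 to 28 - 20 = 8).
- Chemistry: 28 - 15 = 13 days (28 - 17 = 11 to 28 - 13 = 15).

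**3. Interval to the next listed test under the current plan.** Assumption: 6 months is 183 days after day 28, which is day 211, with the ±14-day follow-up window.
- CBC: 211 - 22 = 189 days (197 - 24 = 173 to 225 - 20 = 205).
- Chemistry: 211 - 15 = 196 days (197 - 17 = 180 to 225 - 13 = 212).

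**4. Interval if both tests were drawn on days 39-42** (from the nominal visit days)
- CBC: 39 - 22 = 17 to 42 - 22 = 20 days.
- Chemistry: 39 - 15 = 24 to 42 - 15 = 27 days.
- After the last planned dose: 39 - 28 = 11 to 42 - 28 = 14 days.

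**5. Overlap for responders.** Cycle 2 is to start within 2 weeks of the end of cycle 1 treatment, so by day 28 + 14 = 42. The day 39-42 visit therefore falls 0 to 3 days before a cycle 2 that starts on day 42, and the new tests would partly duplicate the cycle 2 day 1 tests.

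**6. Patients on this path.** The plan gives no expected response rate after cycle 1, so the planning ORR at end of treatment (60% null, 75% target) is used as a rough guide.
- All 62 enrolled, ignoring the futility rule: 62 × (1 - 0.75) = 15.5; 62 × (1 - 0.60) = 24.8.
- Averages from Table 6, which include futility stopping: 53.0 - 39.8 = 13.2 at 75%; 26.9 - 16.1 = 10.8 at 60%.

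This gives roughly 11 to 25 patients. The guide probably runs high, because some final non-responders will have been in CR or PR after cycle 1. In the other direction, the plan states no accrual hold while responses are pending, so enrolment could exceed the Table 6 averages. These figures count patients on the path; they do not count missed toxicities.

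**The case against.** The strongest reply is that monitoring is asked for elsewhere and that the proposed test comes late. Sections 7.1 and 8.1.1.3 ask for close monitoring, CBC is already weekly to day 22, Day 42 has an adverse event evaluation, and related events are followed until they resolve or stabilise. Investigators may order tests at any time. A draw 11 to 14 days after the last dose misses transient abnormalities on days 23-28. Acalabrutinib is short-lived: about 1 hour in section 1.4, and 6.9 hours for the active metabolite in 1.2.3.

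Part of this stands. Transient abnormalities on days 23-28 would still be missed. But 7.1 and 8.1.1.3 name no test and no date, and follow-up of related events begins only once an event has been found. Rituximab persists much longer, with a median terminal half-life of 22 days in NHL patients (1.3.3), so toxicity that is late or slow to clear could still be seen at Day 42.

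A reader might infer more: that the section 14.4 safety rule is materially biased. These patients do stay in the treated population (14.5), and the rule pauses the study above 20%. Exactly 20% (3/15, 6/30, 9/45 or 12/60) does not pause it and one more event does, so a single missed grade 4 event could matter at a boundary. The documents do not support a stronger claim. Under 8.3.1 an abnormal laboratory value is an adverse event only if clinically significant, and 8.3.4 adds values that the investigator judges relevant. After dosing has ended, a silent abnormality cannot qualify by forcing a dose change. It would also have to be grade 4, arise after the last test, last to Day 39-42 and fall at a boundary. The documents give no probability for any of these. The pooled acalabrutinib rates in 8.1 come from a median exposure of 21.9 months and do not transfer to 28 days.

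Nor are these patients without any safety follow-up, given the Day 42 evaluation and the follow-up of related events. Some SD patients may also have month 6 tests under 6.5 and footnote h, though that is too late for cycle 1 toxicity.

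**Conclusion.** The point holds as a gap in the visit schedule. After cycle 1, SD and PD patients have no scheduled CBC after day 22 (±2) and no scheduled chemistry after day 15 (±2). The next listed tests come at month 6 and, under 11.1.2, attendance is not required. The case for change is patient safety: finding a late or persistent cytopenia or organ toxicity at a visit that these patients already attend.

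The number of abnormalities missed cannot be derived from the documents. The patient count rests on using end-of-treatment ORR as a guide to response after cycle 1, and the month 6 interval on a 183-day half-year. Any effect on the section 14.4 rate would be downward, is unquantified and is probably very small. The primary ORR test is not affected. This is a cheap improvement worth making, not a flaw in the trial's inference.

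**What to change.** Add CBC with differential and the serum chemistry panel to the Cycle 1 Day 42 (-3) list in 11.1.2 and to the Day 42 column in 11.2, for all patients, drawn with the existing correlative sample. Response may not be known when the blood is taken, so the tests should not depend on it.

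Leave 6.1.1 unchanged. It ties the ANC and platelet criteria to day 1 of each new cycle, and accepting an older draw would loosen the re-dosing check. One draw serves both purposes only when the Day 42 visit and cycle 2 day 1 fall on the same day.

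The cost is a short schedule amendment and one extra CBC and chemistry panel for at most 62 patients, partly duplicating cycle 2 day 1 tests in responders. No visit is added, and the sample size, primary analysis and stopping rules do not change.
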